#### 4.3. Outcome Measures

**Efficacy outcome measures:** Buntanetap has shown to improve AD participants' cognition. ADAS-Cog 11 and MMSE will be measured to assess its improvement on AD participants' cognition, ADCS-ADL will be measured to assess its improvement on AD participants daily living functions. ADCS-CGIC will also be measured to assess its effect in AD participants' performance. DSST will be measured to assess AD participant's CNS dysfunction.

**Safety outcome measures:** Reports of adverse events (AEs) and serious adverse events (SAEs) during exposure to buntanetap will be collected to evaluate if there are any significant clinical safety issues for the study population. Extensive clinical and laboratory safety data already exist for buntanetap; therefore, these safety measures will be sufficient in the proposed study.

Clinical, functional and cognitive assessment measures: The participants will be administered the MMSE (Folstein 1975) for determination of inclusion into the study. The ADAS-Cog11 (Rosen 1984) and MMSE will be administered for participants' cognitive function. The ADCS-ADL (Galasko 1997) will be administered for participants' daily activity. ADCS-CGIC (Guy 1976) will be administered for participants cognitive and daily functions. The DSST (WAIS-IV; Wechsler 2008) will serve as a sensitive measure of CNS dysfunction.

**Exploratory measures**: Buntanetap has shown to reduce neurotoxic proteins, reduce inflammation and preserve axonal integrity and synaptic functions in previous Phase 2a studies. In this study we potentially plan to measure plasma A $\beta$ 42/42 ratio, GFAP, NFL, p-Tau 181, p-Tau217 and TDP43.

Confidential Page 22 of 57

Ver. 3.1; 09-25-2023

#### 5.1. Risks and Benefits Associated with Buntanetap or Placebo

There are no benefits to the participants other than receiving medical and selective functional and cognitive evaluations.

The clinical investigator must advise all potential participants of the possibility of unexpected side effects and carefully evaluate each person exposed to Investigational Product for possible AEs.

Side effects to placebo are not uncommon but are obviously not due to a pharmacological agent as an industry standard placebo (inactive ingredients) will be provided. The placebo used for the study consists of standard (non-lactose) pharmaceutical excipients which are generally recognized as safe (GRAS), with no known side effects anticipated.

Buntanetap has been tested in animal safety studies. No adverse effects were observed in rats given doses up to 40 mg/kg/day for 26 weeks. Drug-related effects observed in dogs included severe tremors at  $\geq$ 20 mg/kg/day, ataxia, and gastrointestinal erosion/ulcer/inflammation at  $\geq$ 30 mg/kg/day, convulsions at  $\geq$ 60 mg/kg/day, and duodenal necrosis and death at 100 mg/kg (equivalent to a human dose of 3,350 mg). No adverse effects were observed in dogs given doses up to 20 mg/kg/day for 36 weeks.

In clinical studies to date, buntanetap has been well tolerated with single doses of 80 mg or less and QID doses of 60 mg up to 25 days. A higher single dose of 160 mg was associated with an increased incidence of nausea and vomiting. Aside from nausea and vomiting, which are well-known responses to treatment with AChE inhibitors, the only consistent pattern of AEs entailed dizziness/fainting, headache, and reduction in total serum protein. These effects were seen to varying degrees at all doses of buntanetap and in the placebo group. There was a tendency, but no definitive pattern of increased incidence of AEs with increasing dose of buntanetap. There have been no SAEs in prior clinical studies with buntanetap.

Definitive reproductive and developmental toxicity studies have not been conducted with buntanetap. As a result, women of childbearing potential will be excluded from participating in this study unless they agree to be on contraceptive for the whole duration of the trial and four weeks after. Female partners of male participants of childbearing potentials will also need to agree to be on contraceptive for the whole duration of the trial plus an additional four weeks. Male study participants should not donate sperm and female study participants should not donate eggs during the whole duration of the trial and four weeks after.

At this time, there is no controlled clinical data available for anyone receiving SARS-CoV-2 (COVID19) vaccination while being treated with buntanetap. However, based on the intended mechanism of actions and currently available data for these vaccine candidates and for buntanetap, it is not believed that there are specific risks to consider in participants participating in this study who have received SARS-CoV-2 (COVID19) vaccination or who are planning to

Confidential Page 23 of 57

receive the vaccination. As such, SARS-CoV-2 (COVID19) vaccination is not prohibited. If appropriate, SARS-CoV-2 (COVID19) vaccination should be considered as a concomitant medication

#### 5.2. Risk/Benefit Associated with Blood Collections

Phlebotomy is associated with mild to moderate discomfort due to piercing of the skin. This can be minimized with the use of a well-trained phlebotomist/nurse. Sometimes the blood draw site may become discolored with a "bruised" appearance that is transient and not painful. Rarely, the blood draw site may become infected and require antibiotic treatment.

#### 6.0 SAMPLE SIZE AND STATISTICAL PLAN

A sample size of up to 320 participants (1:1:1:1 randomized to 7.5mg, 15mg, 30mg buntanetap and placebo respectively) is planned to be randomized.

Definitions of the analysis populations and a detailed description of the analysis rules will be presented in a separate Statistical Analysis Plan (SAP).

#### 6.1. Randomization

Participants who have signed an informed consent and meet screening eligibility requirements will be randomly assigned to the active and placebo treatment groups at 1:1:1:1 ratio. The randomization methodology used is permuted block randomization.

# 6.2. Power and Sample Size Determination

Qualified participants will be randomized at a 1:1:1:1 ratio to one of the following three treatment groups: 7.5 mg, 15 mg, 30 mg QD buntanetap and placebo. A sample size of 280 (210 combining all three buntanetap-treatment groups and 70 in control) will have a 90% power to detect a treatment difference for the primary efficacy variable ADAS-Cog11 at a two-sided significance level of 0.05, assuming a delta of 2.7 between the treatment (pooling all three treatment arms together) and placebo, and a common standard deviation of 6.0. This sample size will also have an 89% power to detect a significant difference for the co-primary efficacy variable ADCS-CGIC at a two-sided significance level of 0.05, assuming a delta difference 0.23 between the treatment (pooling all three treatment arms together) and placebo, and a common standard deviation of 0.5. Approximately 320 participants will be randomized (approximately 80 per arm) to account for an expected 12.5% dropout rate.

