# 6.10.1 Re-estimation of Sample Size

The initial planned sample size was determined for ADAS-Cog11 based on a targeted power of 90% to detect a delta of 2.7 between the treatment (pooling three arms together) and placebo, with a common standard deviation of 6.0 at a two-sided significance level alpha of 5%. This sample size will also have a power of 89% to detect a significant difference for the co-primary effectiveness variable ADCS-CGIC at a two-sided significance level of 5%, assuming a delta of 0.22 with a common standard deviation of 0.5. Accounting for an expected drop-out rate of 12.5%, a sample size of approximately 320 participants (80 per treatment arm) was calculated to achieve 280 evaluable participants (70 per treatment arm).

To guarantee sufficient power for the primary trial objectives, sample size will be re-estimated based on the calculated conditional power at the interim analyses. The conditional power for each co-primary endpoint will be calculated at the significance level of 0.05 separately, according to the methodology and equation from Mehta and Pocock (2011). The sample size will only be increased if the conditional powers for both co-primary endpoints are >50% (and <90%), otherwise, the trial will continue as planned, i.e., no decrease in sample size or stopping the trial early for futility or efficacy success at the interim analysis. The target power is 90% and maximum sample size per group is set to be 100 participants per arm. Specifically, if both conditional powers at interim analysis are >50%, then each arm will be increased to 100 participants. Otherwise, the trial will continue as is.

Chen, Lan and Demets (2004) have shown that, when conditional power  $\geq 50\%$ , one may increase sample size to n2\* and the conventional test statistics and critical values can be used at the final analysis, the overall type I error rate will not be inflated. Further, Chen, Yuan and Li (2018) demonstrated that the conventional maximum likelihood estimate, and coverage error of its conventional confidence interval are generally small following sample size adjustment. Therefore, conventional point estimate and confidence interval are recommended to be used when applying the 50% conditional power principle for sample size re-estimation, to keep consistent statistics in both hypothesis test and statistical inference.

Confidential Page 29 of 57

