Statistical Analysis Plan Version 2.0, 27 February 2024

1 Abbreviations

 $\begin{array}{ll} \alpha SYN & Alpha-synuclein \\ A\beta & Amyloid \ beta \end{array}$

AD Alzheimer's disease

ADAS-Cog Alzheimer's Disease Assessment Scale-Cognitive Subscale

ADCS-ADL Alzheimer's Disease Cooperative Study—Activities of Daily Living Scale

ADCS-CGIC Alzheimer's Disease Cooperative Study—Clinical Global Impression of

Change

AE Adverse Event

APP Amyloid β Precursor Protein AR(1) First-order Autoregressive

ATC Anatomical Therapeutic Chemical

AUC Area under the curve

C_{max} Maximum plasma and CSF concentration

CI Confidence interval

CL Clearance

CM Concomitant medication
CSF Cerebrospinal Fluid
CSP Clinical Study Protocol

C-SSRS Columbia Suicide Severity Rating Scale

CV Coefficients of variation

DSMB Data Safety Monitoring Board
DSST Digital Symbol Substitution Test

ECG Electrocardiogram

eCRF Electronic Case Report Form

ES Enrolled set

FDA Food and Drug Administration
GFAP Glial Fibrillary Acidic Protein

IC Informed Consent

IMP Investigational Medicinal Product iSAP interim Statistical Analysis Plan

ITT Intent-to-Treat set
LSM Least Square Mean
MAR Missing at Random

MCMC Markov Chain Monte Carlo

MedDRA Medical Dictionary for Regulatory Activities

mITT Modified Intent-to-Treat set

MMRM Mixed Model for Repeated Measures

MMSE Mini-Mental State Examination

MNAR Missing Not at Random NFL Neurofilament Light Phosphorylated tau p-tau PDParkinson's disease PΚ Pharmacokinetic PPS Per-protocol set PT Preferred Term QD Once a Day

SAE Serious Adverse Event
SAF Safety analysis set
SAP Statistical Analysis Plan
SD Standard Deviation
SOC System Organ Class

TEAE Treatment-Emergent Adverse Event

T_½ Half-life tau Tau protein

TDP-43 TAR DNA-binding Protein 43 t_{max} Time to peak drug concentration

TOEPH Heterogeneous Toeplitz

UN Unstructured

WHO World Health Organization

2 Document Version History

Version Number	Version date	Section(s) Updated	Change since previous version (with reason)
Final 1.0	16-JAN-2024	All	Final version
Final 2.0 Amendment	27-FEB-2024	Section 8.8	Missing data algorithm was added on item scores of co-primary endpoint ADAS-Cog11 as a sensitivity analysis

3 Introduction

This Statistical Analysis Plan (SAP) is based on Clinical Study Protocol (CSP) Version 3.1, dated September 25, 2023. In the case where there is a difference between the protocol and the SAP, the SAP will be the ruling document.

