Participants who have signed an informed consent and meet screening eligibility requirements will be randomly assigned at a 1:1:1:1 ratio to one of the four treatment arms: buntanetap 7.5 mg, buntanetap 15 mg, buntanetap 30 mg, and placebo, through an Interactive Randomization System, after a screening period of up to 42 days, followed by an at home dosing period of 12 weeks. Participants will be required to visit clinics at Day 0 (baseline), 6 weeks, and 12 weeks (end-of-trial), where they will undergo study procedures that include safety assessments (AE and concomitant medication monitoring, 12-lead ECGs, clinical laboratory testing, vital signs assessments, and physical/neurological examinations), and psychometric tests (ADAS-Cog11, ADCS-CGIC, ADCS-ADL, DSST, MMSE).

The Schedule of Events is shown in Appendix 1.

6 Determination of Sample Size

A sample size of up to 320 participants (1:1:1:1 randomized to 7.5 mg, 15 mg, 30 mg buntanetap and placebo respectively) is planned to be randomized.

Qualified participants will be randomized at a 1:1:1:1 ratio to one of the following four treatment groups: 7.5 mg, 15 mg, 30 mg QD buntanetap and placebo. A sample size of 280 (210 combining all three buntanetap-treatment groups and 70 in control) will have 90% power to detect a treatment difference for the co-primary efficacy variable ADAS-Cog11 at a two-sided significance level of 0.05, assuming a delta of 2.7 between the treatment (pooling all three treatment arms together) and placebo, and a common standard deviation (SD) of 6.0. This sample size will also have an 89% power to detect a significant difference for the co-primary efficacy variable ADCS-CGIC at a two-sided significance level of 0.05, assuming a delta difference 0.23 between the treatment (pooling all three treatment arms together) and placebo, and a common SD of 0.5. Approximately 320 participants will be randomized (approximately 80 per arm) to account for an expected 12.5% dropout rate.

7 Data Sets to be Analyzed

The following analysis sets will be used for the statistical analysis and presentation of data:

- The Enrolled analysis set (ES) will include all participants who signed IC and meet all inclusion
 and exclusion criteria. All data collected from ES will be presented in listings and if relevant in
 tables and/or graphs. Screening failures will have selected data be presented in a separate
 listing if needed.

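### The 89% power for ADCS-CGIC is paired with a difference of 0.23 in two places and 0.22 in a third; at the printed SD only 0.22 gives 89%

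*Protocol*

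**What the plan says.** Protocol 6.2 plans 280 evaluable participants, 210 in the three buntanetap arms pooled and 70 on placebo. For ADAS-Cog11 it gives 90% power at two-sided 0.05, "assuming a delta of 2.7 between the treatment (pooling all three treatment arms together) and placebo, and a common standard deviation of 6.0". For the other co-primary endpoint it adds: "This sample size will also have an 89% power to detect a significant difference for the co-primary efficacy variable ADCS-CGIC", at the same significance level, "assuming a delta difference 0.23 between the treatment (pooling all three treatment arms together) and placebo, and a common standard deviation of 0.5".

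SAP section 6 gives the same 89%, "assuming a delta difference 0.23 between the treatment (pooling all three treatment arms together) and placebo, and a common SD of 0.5".

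Protocol 6.10.1 restates the basis of the initial sample size, with the same 280 evaluable participants (70 per arm). It says: "This sample size will also have a power of 89% to detect a significant difference for the co-primary effectiveness variable ADCS-CGIC", again at two-sided 5%, but "assuming a delta of 0.22 with a common standard deviation of 0.5".

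SAP section 3 provides that where protocol and SAP differ, "the SAP will be the ruling document".

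**The concern.** One design has one planning difference per endpoint. Here N, allocation, SD, significance level and power are the same in all three places, and only the difference changes. Protocol 6.10.1 describes the initial plan, so 0.22 is not a revised assumption made after the interim analysis. All three statements are current text.

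The figures in Protocol 6.2 and SAP section 6 also look out of order among themselves. As printed, ADCS-CGIC has the larger standardised effect of the two co-primary endpoints but the lower power, in the same 210 versus 70 comparison.

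What is at stake is whether the sample-size justification can be checked. Both co-primary endpoints must be significant before the secondary endpoints are tested confirmatorily (SAP 8.2.1), so a reader of the results will want to know what effect on ADCS-CGIC the trial was planned to detect. The documents give two answers.

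**Working it through.** **Inputs.** n = 210 and 70; two-sided alpha 0.05; ADAS-Cog11 difference 2.7 and SD 6.0; ADCS-CGIC SD 0.5 (Protocol 6.2, SAP 6). ADCS-CGIC difference 0.23 (Protocol 6.2, SAP 6) or 0.22 (Protocol 6.10.1).

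**Formula.** z = difference / (SD × √(1/210 + 1/70)), where √(1/210 + 1/70) = 0.1380. Power ≈ Φ(z − 1.96). The t-test figure uses the noncentral t distribution with 278 degrees of freedom.

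**The plan's own figures first.** For ADAS-Cog11, z = 2.7/(6.0 × 0.1380) = 3.261, so power is Φ(1.301) = 90.3% (t: 90.1%). The stated 90% reproduces. The dropout allowance does too: 280/0.875 = 320.

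**ADCS-CGIC, SD 0.5.**

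| Difference | Source | Standardised effect | z | Power, normal | Power, t | Stated |
|---|---|---|---|---|---|---|
| 0.23 | Protocol 6.2, SAP 6 | 0.46 | 3.333 | 91.5% | 91.3% | 89% |
| 0.22 | Protocol 6.10.1 | 0.44 | 3.188 | 89.0% | 88.8% | 89% |

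**Order of the two endpoints.** The standardised effect for ADAS-Cog11 is 2.7/6.0 = 0.45. At 0.23 the ADCS-CGIC effect is 0.46, so its power should be above that of ADAS-Cog11, yet 89% is printed against 90%. At 0.22 the effect is 0.44 and the order is right.

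**Could the difference have been rounded to 0.23?** Values from 0.225 to 0.235 give z from 3.261 to 3.405 and power from 90.3% to 92.6% (t: 90.1% to 92.4%). None gives 89%. At SD 0.5 the difference for exactly 89% is 0.2199 (normal) or 0.2207 (t).

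**Could N differ?** At 0.23 and SD 0.5 with 3:1 allocation, 89% power needs a total of 256 (normal) or 258 (t), not 280. Using all 320 randomised participants gives 94.4% (t).

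**Could the test differ?** A one-sided 0.05 test gives 95.4%. A rank test, with an assumed relative efficiency of 0.955 that is not in the documents, gives about 90.3%.

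**Could the SD have been rounded to 0.5?** At 0.23, 89% needs an SD of about 0.521 (t). With SD 0.52 the normal approximation gives z = 0.23/(0.52 × 0.1380) = 3.205 and power 89.3%. At that same SD, 0.22 gives z = 3.066 and power of about 86.5%, so the statement in Protocol 6.10.1 would then fail.

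**The case against.** The strongest counter-argument is rounding of the SD. It is printed to one decimal, so 0.5 could stand for anything from 0.45 to 0.55, and an SD near 0.52 would make 89% right at 0.23. The standardised effect would then be 0.23/0.52 = 0.442, below the 0.45 for ADAS-Cog11, and the order of the two powers would also be right. On that reading the figures in Protocol 6.2 and SAP section 6 are coarsely printed, not wrong.

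This stands as a possibility and is a reason to ask for the unrounded SD. It does not remove the problem. Nothing in the documents says that the SD was rounded, a reader cannot recover 89% from what is printed, and the same SD puts the 0.22 pair at about 86.5%. No single SD gives 89% at both differences.

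The SAP's precedence rule is a second objection. It makes 0.23 the governing difference, but it does not make 89% follow from it.

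The third objection is that little depends on the point. That is correct. The gap is 2.3 to 2.5 percentage points in a two-sample approximation, while the planned analysis is an MMRM. Protocol 6.10.1 says that the sample size was determined on ADAS-Cog11, and SAP 8.9 records that the interim re-estimation has been done.

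**Conclusion.** The concern holds, as a minor one. The planning difference for a co-primary endpoint is given as both 0.23 and 0.22 for the same N, SD, significance level and power. At the printed SD of 0.5 only 0.22 yields 89%; 0.23, the value in the ruling document, yields about 91%. The arithmetic favours 0.22, but the documents do not show which figure is the slip.

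If 0.23 was intended, the stated power is understated by about 2.5 points, which is conservative. If 0.22 was intended, the power is right and the difference is misprinted in two places. Either way the trial has roughly 89% to 91% power for ADCS-CGIC on its own assumptions, and no sample size, test or decision changes.

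These figures assume a fixed-size two-sample comparison of means with the SD exactly as printed. They are not MMRM power calculations, but the same approximation reproduces the plan's ADAS-Cog11 figure.

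**What to change.** Use one reproducible set of difference, SD and power in Protocol 6.2, Protocol 6.10.1 and SAP section 6. Either:

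- state 0.22 with 89%, which changes the difference in Protocol 6.2 and SAP 6; or
- state 0.23 with about 91%, which changes the power in all three places and the difference in Protocol 6.10.1.

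If the original calculation used an SD that was later rounded to 0.5, print the unrounded SD that makes the chosen pair agree. The original sample-size calculation should settle which option applies.

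The cost is one or two numbers in each place. Because Protocol 22.2 requires IRB approval before an amendment is put into use, the protocol correction can be recorded in a clarifying note rather than in an amendment of its own.

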# 6.3. Safety and Tolerability Analysis

Safety and tolerability will be assessed with physical examinations, vital signs, clinical laboratory values, 12-lead ECG, use of concomitant medications, and AE reports. The frequencies of adverse events, serious adverse events, and laboratory abnormalities between the participants across the treatment groups will be compared.

Confidential Page 24 of 57

Participants who dropout during the initial 9 weeks at-home treatment period will be discontinued and invited to an Early Discontinuation visit. Participants that drop out after the initial 9 weeks will be scheduled for an end-of-trial visit. If 4 participants are discontinued due to serious adverse events a DSMB safety review will be conducted without interrupting the study.

